#### 5.5.2 Specific objectives

- Describe the safety of the ophthalmic gel PRO-167 by means of the density of goblet cells
- Describe the safety of the ophthalmic gel PRO-167 by means of changes in ocular surface stains.

- Describe the safety of the ophthalmic gel PRO-167 by means of changes in intraocular pressure.
- Describe the safety of the ophthalmic gel PRO-167 by means of changes in laboratory tests.
- Describe the safety of the ophthalmic gel PRO-167 by means of changes in vital signs.
- Describe the safety of the ophthalmic gel PRO-167 by means of changes in visual ability.
- Describe the safety of the ophthalmic gel PRO-167 by means of changes in the time of tear rupture.
- Describe the safety of the ophthalmic gel PRO-167 by means of changes in the ocular comfort index.
- Describe the safety of the ophthalmic gel PRO-167 by means of changes in the posterior segment.
- Describe the safety of the ophthalmic gel PRO-167 by means of changes in ophthalmological signs and symptoms.
- Describe the safety of the ophthalmic gel PRO-167 when assessing the integrity of the anterior segment by means of the green lysine stain.
- Describe the safety of the ophthalmic gel PRO-167 by means of the presentation of adverse events.

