#### 6.6.1 Calculation of the sample size

Although there are no references on the calculation of the sample size in phase I studies, it was considered pertinent to perform it according to the presentation of adverse events referred by Christ T, in a randomized controlled trial of parallel groups, single blind, with randomization where

it was evaluated the efficacy and tolerance of a 5% dexpanthenol ophthalmic gel versus a 5% panthenol ointment in 48 subjects with corneal erosion, keratoconjunctivitis by UV radiation or similar conditions. The intervention consisted in the application of 1 cm of the gel and the ointment during 4 and 3 days, respectively. [20]

The percentage of good tolerance that was presented with the gel was 25%, so it is expected that no more than 10% of the subjects report a bad tolerance with the formulation proposed in this protocol.

The sample size was calculated using the formula for proportions

$$n = p (1 - p) \left( \frac{Z_{1-\alpha + Z_{1-\beta}}}{p - p0 - \delta} \right)^2$$

With a statistical confidence of 95% corresponding to the type I error, equal to 1.96, with a power of 80%, corresponding to the type II error, equal 0.84.

According to the previous calculation, the result is 19 subjects, which was increased by 20% for the probable losses. The total sample size required is 24 subjects. Therefore, each group will consist of 12 subjects, who will provide an eye for analysis.

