#### 8.3 Statistical methodology

#### 8.3.1 Analysis of primary and secondary outcome variables

The statistical analysis will be carried out by personnel of Sophia Laboratories. The statistical program SPSS version 19 (IBM Corporation, Armonk, NY, USA) will be used.

The designated personnel will be blinded to the intervention groups. The coding will be done using consecutive numbers for each intervention group.

The data will be collected and sorted in an excel sheet. Later they will be exported to the platform of the SPSS program. The variables will be categorized according to their nature.

The result of the continuous quantitative variables will be presented in measures of central tendency: mean, standard deviation and ranges. See Table 4. Scales to be used

The normal distribution of the results will be obtained by the Kolmogorov-Smirnov test.

The statistical analysis of the continuous **quantitative variables** to find significant differences (p) will be the following:

- Intra-group analysis: Wilcoxon rank test.
- Inter-group analysis: Mann-Whitney U test.

The level of difference to consider significance will be an alpha of 0.05 or less.

The result of nominal and ordinal qualitative variables will be presented in frequencies, proportions and percentages.

The statistical analysis to identify significant differences of the **qualitative variables** will be done creating 2x2 contingency tables and it will be carried out in the following way:

- Intra-group difference: McNemar or Pearson test.
- Difference between groups: test χ2 (Chi-square) of Pearson.

The level of difference to consider significance will be an alpha of 0.05 or less.

For the reporting of adverse events all eyes of those participants who were randomly assigned to an intervention group after the baseline visit will be considered. The results will be expressed in number of cases (eyes).

The final report of the results will be shown in tables or graphs, as appropriate.

It will be considered that the investigational drug is safe and tolerable when there are no clinical and statistical differences in all the variables of primary outcome, with respect to its comparator.

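### Section 8.3.1 offers a Pearson test as an unrestricted alternative to McNemar for within-group comparisons, although the readings are paired and Pearson is not valid for them

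*Combined protocol and SAP*

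**What the plan says.** Section 8.3.1 states that the analysis of qualitative variables "will be done creating 2x2 contingency tables and it will be carried out in the following way". It then gives two lines. The within-group line is "Intra-group difference: McNemar or Pearson test". The between-group line is "Difference between groups: test χ2 (Chi-square) of Pearson". Nothing says when Pearson replaces McNemar within a group, or what the rows and columns of the within-group table are.

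For continuous variables the same section has "Intra-group analysis: Wilcoxon rank test", with Mann-Whitney between groups. The significance criterion is "The level of difference to consider significance will be an alpha of 0.05 or less".

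On the data, Section 6.6.1 says "Therefore, each group will consist of 12 subjects, who will provide an eye for analysis". The schedule in Section 6.5 has ocular signs and symptoms recorded at baseline, visit 1 and the final visit. Section 5.5.2 includes the objective "Describe the safety of the ophthalmic gel PRO-167 by means of changes in ophthalmological signs and symptoms". Section 8.3.2 applies the methods of the full analysis to a partial analysis at 4 subjects per group.

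**The concern.** Within a group, each eye is compared with itself at another visit, so the two readings are paired. McNemar is built for this: it asks whether the proportion with a sign has shifted, using only the eyes that changed state. Pearson's chi-square is for independent observations. Which question it answers on paired data depends on a layout that the plan does not define, and neither layout gives a valid test of paired change.

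The plan appears to respect pairing for continuous variables, if its Wilcoxon test means the signed-rank test. The Pearson option departs from that for qualitative variables. These include burning, foreign body sensation and itching, which are primary tolerability outcomes (Section 6.4.1.2) and are typed nominal in Table 4.

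At stake is whether the p-values attached to within-group changes mean what a reader will take them to mean. Because the choice of test is open, it could also be made after the data are seen.

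**Working it through.** The documents state no p-value, power or error rate for the within-group test, so there is no figure of the plan's own to reproduce. The check compares the two permitted tests on the same data.

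**Inputs.** 12 eyes per group, one per subject (Section 6.6.1), and alpha 0.05 (Section 8.3.1). Assumed: two-sided tests, Pearson without continuity correction, and all 12 pairs complete.

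**Notation.** a = absent at both visits; b = absent then present (new); c = present then absent (resolved); d = present at both visits; n = a + b + c + d.

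**Formulas.**
- Pearson on the baseline-by-follow-up table: chi2 = n(ad − bc)² / [(a+b)(c+d)(a+c)(b+d)], 1 df.
- Exact McNemar: p = 2 × P(Bin(b+c, 0.5) ≤ min(b, c)), capped at 1.
- Pearson on the visit-by-status table: the same chi-square on the rows (a+b, c+d) and (a+c, b+d), total 2n.

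**Layout 1: baseline by follow-up.**
- *No eye changes*, (a, b, c, d) = (9, 0, 0, 3): chi2 = 12 × 27² / (9 × 3 × 9 × 3) = 12.0, p = 0.0005. McNemar has no discordant pairs, p = 1. With b = c = 0 and both states present, chi2 always equals n, so the result is the same for every split from 11/1 to 1/11.
- *Six eyes worsen, none improve*, (5, 6, 0, 1): chi2 = 12 × 5² / (11 × 1 × 5 × 7) = 300/385 = 0.78, p = 0.38. Exact McNemar: 2 × 0.5⁶ = 0.031. For the other computable splits with b = 6 and c = 0, Pearson p lies between 0.25 and 0.38.
- *All eyes absent at baseline, six worsen*, (6, 6, 0, 0): c + d = 0, so the denominator is zero and Pearson cannot be computed. Exact McNemar is still 0.031.
- *How general this is*: of the 455 possible tables with n = 12, the two tests give different verdicts at 0.05 in 178, counting a non-computable Pearson as not significant.

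**Layout 2: visit by status.**
- (3, 6, 1, 2), that is 3/12 present at baseline and 8/12 at follow-up: chi2 = 24 × (9 × 8 − 3 × 4)² / (12 × 12 × 13 × 11) = 86,400/20,592 = 4.20, p = 0.04. Exact McNemar on 6 against 1 discordant pairs: 2 × (1 + 7)/128 = 0.125. Part of this gap comes from the exact calculation: asymptotic McNemar gives chi2 = 25/7 = 3.57, p = 0.059, which is still above 0.05.
- This layout does respond to change. With no change it gives p = 1. With 0/12 against 6/12 it gives chi2 = 8.0, p = 0.0047, against 0.031 for exact McNemar. Its fault is counting 12 pairs as 24 independent readings.

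**Partial analysis, n = 4.** No change, (2, 0, 0, 2), layout 1: chi2 = 4 × 4² / (2 × 2 × 2 × 2) = 4.0, p = 0.0455, nominally significant. McNemar gives p = 1.

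**The case against.** The best defence has four parts.

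1. *McNemar is listed, and the more striking failures need one particular layout.* This stands in part. A reader might infer that the plan's within-group test will call unchanged eyes significant, or miss a worsening in half of them. The documents do not support that as a certainty: they permit the wrong test without requiring it, and the table is undefined. Because the text asks for a within-group difference, the visit-by-status layout is a natural reading, and there both of those failures disappear. The ignored pairing remains, so Pearson is not valid there either.

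2. *The safety conclusion does not depend on these tests.* This stands. A reader might infer that the Pearson option undermines the verdict on the product. Section 8.3.1 bases that verdict on differences from the comparator, the hypothesis in Section 5.5.3 is comparative, and the Summary lists only between-group tests. The objectives in Section 5.5.2 speak of describing changes and require no within-group significance test.

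3. *The no-change example needs some eyes positive at baseline.* This is fair. Subjects must be ophthalmologically healthy (Section 6.2.1), so all-absent baselines are likely for many signs. In layout 1 Pearson then gives no result at all, which is a failure of a different kind.

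4. *The analysts are blinded to group (Sections 7.4 and 8.3.1).* This limits steering towards one arm. It does not stop a choice of test after within-group results have been seen under coded labels.

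It would also be too strong to say that a Pearson p-value has the opposite meaning. It answers a different question.

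**Conclusion.** Wrong as written, with moderate consequences. Section 8.3.1 names a test that is not valid for paired readings as a free alternative to one that is. At the planned 12 eyes per group the choice can move a result from p = 1 to p = 0.0005, or from 0.031 to 0.38, on a baseline-by-follow-up table. On a visit-by-status table it can move a result from 0.125 to 0.04. These figures rest on the assumptions stated with the inputs, and the tables are illustrations, not predictions.

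The effect falls on the supportive within-group results behind the objectives about changes, and on the partial analysis. Section 9.2 lets the partial analysis inform a decision on early termination, but none of the termination grounds listed there is a within-group p-value. The between-group conclusion is unaffected.

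**What to change.** Amend the within-group line for qualitative variables in Section 8.3.1 as follows:

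- Delete the Pearson option.
- For binary variables, such as chemosis, specify the exact two-sided McNemar test and report the numbers of new and resolved cases beside each p-value.
- For burning, foreign body sensation and itching (five severity and five frequency levels, Section 6.4.3.9) and for hyperaemia (five grades, Table 4), specify a paired ordinal method such as the Wilcoxon signed-rank test. If a graded variable is to be put into a 2x2 table, state the cut-point in advance and use exact McNemar. Without this, deleting Pearson leaves the graded variables without a defined analysis.
- In Section 8.3.2, present the within-group results of the partial analysis descriptively. With 4 pairs the smallest possible exact McNemar p is 2 × 0.5⁴ = 0.125, so significance at 0.05 cannot be reached.

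The cost is a few lines of wording. No additional data, visits or subjects are needed, and McNemar is already named in the plan.

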#### Number of patients:

24 subjects, divided into 2 groups [12 eyes exposed per group]

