#### 6.3 Intervention

# 6.3.1 Managed treatments

# 6.3.1.1 Treatment under study

#### PRO-167

- o Active ingredients: Dexpanthenol 5%
- o Pharmaceutical form: Ophthalmic gel.
- o Prepared by: Sophia Laboratories A.S. of V.C.
- Posology: a strip approximately 1 cm long, 4 times a day during the waking period, in the bottom of the right eye sac.
- Description of the formulation: transparent gel, free of visible particles.
- o Description of the packaging: sterile multi-dose tube, low density polyethylene polyethylene and aluminum with high density polyethylene lid.

Table 3. Quali-quantitative formulation of PRO-167

Type of agent	Amount mg/mL	Function
Dexpanthenol	50.0	Active principle (lubricant)
Boric acid	2.00	Active principle
Sodium Borate decahydrate	without showing	additive
Polysorbate 80	without showing	additive
Sorbitol	without showing	additive
Potassium chloride	without showing	additive
Sodium chloride	without showing	additive
Magnesium Chloride hexahydrate	without showing	additive
Water for the preparation of injectables c.b.p.	1.00	Vehicle

Quali-quantitative formulation of the product under investigation PRO-167. The concentration of the active principles is shown, as well as the substances that act as a buffer additive.

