# 6.4 Outcome variables

# 6.4.1 Security variables

# 6.4.1.1 Primary outcome variables

- Globet cell density
- Epithelial defects in cornea and conjunctiva.
- Presence of adverse events.

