#### 9.3.1.1 Record of adverse events in the Case Report Form

The registry of adverse events considers the information concerning the identification data of the participating patient as code, age, sex, left eye, right eye.

Information about the type of adverse event, adverse reaction or suspected adverse reaction to the product under investigation or to the study medication, as appropriate. The date on which the adverse event occurs is reported, as well as in which the Investigator is aware of it, date of resolution or outcome, as applicable. The clinical diagnosis is indicated. Include in concomitant medications the therapy used for the pharmacological management of the adverse event, suspected adverse reaction, adverse reaction. Record the outcome or resolution of the event: patient recovered without sequelae, with sequelae, not recovered. Patient who presented death due to adverse reaction / adverse event, patient who presented death and it is judged that the drug could have contributed, patient who presented death and this is not related to the investigational product or drug, or indicate that it was not He knows what the consequence of the event is.

Consign information about the product or drug under investigation or the drug associated with the adverse event, adverse reaction or suspected adverse reaction. As applicable, information concerning generic denomination, distinctive denomination or product code in research and / or investigational medication should be recorded, as appropriate according to the methodological design of the study, this is relevant in the case of blinded studies or those where they use placebo as comparators, since there are circumstances that justify opening the cecum to determine if the adverse event, the adverse reaction or suspected adverse reaction may be attributable to the active agent, the combination of active agents, or the substance (s). s) pharmacologically inert (s), such as vehicles or additives, as appropriate the phase of clinical research in which the development of the drug is located. It will also be necessary to record the data concerning the batch number, manufacturer laboratory, expiration date, dosage, route of administration, start and end dates of administration and / or consumption, reason for the prescription; according to whether it is a Sophia Laboratories A.S. of V.C.

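### Adverse events, a primary variable, are counted in eyes, on a literal reading both eyes of every subject, although only the right eye is dosed; the analysis should be per subject

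*Combined protocol and SAP*

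**What the plan says.** Section 6.4.1.1 lists "Presence of adverse events" among the three primary safety variables. Section 8.3.1 calls the product safe and tolerable when no primary variable differs, clinically or statistically, from the comparator.

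For this variable, section 8.3.1 gives a rule of its own: "For the reporting of adverse events all eyes of those participants who were randomly assigned to an intervention group" after the baseline visit are taken into account, and "The results will be expressed in number of cases (eyes").

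Other sections use a different unit:

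- **Dosing.** Sections 6.3.1.1 and 6.3.1.2 place the gel "in the bottom of the right eye sac" in both arms; the Summary agrees.
- **Exposure.** The Summary gives "24 subjects, divided into 2 groups [12 eyes exposed per group" in brackets, and section 6.6.1 says "each group will consist of 12 subjects, who will provide an eye for analysis".
- **Early termination.** Section 9.2 sets its serious-event threshold as a percentage of participants in each group.
- **Non-ocular events.** The end of section 9.3.1.3 expects mostly ophthalmic events but allows for systemic ones.
- **Recording.** Section 9.3.1.1 asks for "identification data of the participating patient as code, age, sex, left eye, right eye", so laterality is captured.
- **Variable type.** Table 4 (section 6.4.3) lists adverse events twice, as a discrete number of cases and as a nominal present/absent item.

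**The concern.** The unit of observation for a variable that decides the safety verdict should match the unit that is randomised and exposed. Here that is the subject, with one treated eye each. Taken at its word, section 8.3.1 does three things that do not fit this design. It brings in left eyes that never receive product. It allows one subject with a bilateral event to count twice. It gives a systemic event no eye to be counted in.

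Left-eye data will exist: visual acuity (6.4.3.1) and staining (6.4.3.4.1) are both taken in each eye. Two analysts could follow the same sentence and report different percentages and, in some data sets, different test results.

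**Working it through.** **Inputs.** 24 subjects, 1:1 allocation, one treated eye each (Summary, 6.6.1, 7.1). Between-group test for qualitative variables: Pearson chi-square on 2x2 tables, alpha 0.05 (8.3.1). The event counts, event rates and between-eye agreement below are illustrative assumptions; the plan gives none for adverse events.

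**Step 1. The plan's own figure.** 24 subjects x 1 treated eye / 2 groups = 12 exposed eyes per group, as the Summary states. Counting both eyes would give 12 x 2 = 24 per group. The plan does not print that figure.

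**Step 2. Formula.** For a and b events in two arms of n units each, with s = a + b, uncorrected Pearson chi-square is

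X² = 2n(a − b)² / [s(2n − s)].

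**Step 3. Worked example, 4 v 0 subjects with an event.**

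| Counting rule | Table | X² | p |
|---|---|---|---|
| Per subject or treated eye | 4/12 v 0/12 | 24·16/(4·20) = 4.80 | 0.028 |
| Both eyes, events in treated eye only | 4/24 v 0/24 | 48·16/(4·44) = 4.36 | 0.037 |
| Both eyes, every event bilateral | 8/24 v 0/24 | 48·64/(8·40) = 9.60 | 0.002 |

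In the second row the rate falls from 33.3% to 16.7%. In the third row X² is exactly twice the per-subject value, because each subject's result has been entered twice.

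**Step 4. Examples where the verdict changes.**
- Treated-eye events: 8/12 v 3/12 gives X² = 600/143 = 4.20, p = 0.041. Over both eyes, 8/24 v 3/24 gives 1200/407 = 2.95, p = 0.086, and the rate in the first arm falls from 67% to 33%.
- Bilateral events: 3/12 v 0/12 gives X² = 216/63 = 3.43, p = 0.064. Counted twice, 6/24 v 0/24 gives 1728/252 = 6.86, p = 0.009.

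**Step 5. Rejection probabilities.** These come from exact binomial enumeration over all outcomes at 12 subjects per arm.

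| True rates | Per subject | Both eyes, treated-eye events only | Both eyes, all events bilateral |
|---|---|---|---|
| 10% v 10% (type I error) | 1.5% | 1.5% | 21.2% |
| 25% v 25% (type I error) | 4.4% | 3.8% | 17.6% |
| 25% v 10% (power) | 12.4% | 12.1% | – |
| 50% v 10% (power) | 60% | 54% | – |

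No power is shown in the last column, because its type I error is not controlled. For partial between-eye agreement of 0.3 to 0.8 (assumed), with both eyes at the same event rate, simulation gives type I error of about 8% to 16%.

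**Step 6. The benign reading.** If all eyes means all exposed eyes, the denominator is 12 per group, equal to subjects, and nothing changes for ocular events in the treated eye. Systemic events still have no unit.

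**The case against.** The strongest reply is that the sentence defines a population rather than a denominator. It stands shortly before the rule limiting the main analysis to adherence above 60%, so its purpose may simply be that everyone randomised counts for adverse events. With 12 exposed eyes per group stated in the Summary, all eyes could mean all study eyes. The text is also a rough translation, and a laterality field on the event form does not make both eyes a denominator.

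Much of this stands. A reader might infer that adverse-event rates will be computed over 24 eyes per group and that the chi-square test will treat fellow eyes as independent. The documents do not say so: section 8.3.1 gives a count, not a rate; the sentence concerns reporting; and Table 4 also carries a present/absent item that could be analysed by subject.

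The examples in step 4 are also selected. With events in treated eyes only, moving from 12 to 24 changes the chi-square verdict for only 10 pairs of counts (ignoring which arm is higher), and each needs events in at least 7 of 12 subjects in one arm. The 3/12 v 0/12 table has a smallest expected count of 1.5, and Fisher's exact test gives p = 0.22 there. Full bilaterality is an extreme assumption when one eye is dosed.

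The reply does not remove the point. The words as written cover all eyes of a participant, without restriction to exposed or study eyes. Even the benign reading leaves systemic events without a unit and does not align the rule with section 9.2.

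**Conclusion.** The point holds as a conflict in the stated unit for a primary variable. Section 8.3.1 counts adverse events in eyes and literally includes untreated ones, against dosing, exposure and early-termination rules that rest on one eye per subject or on participants. It should be corrected before analysis.

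The size is conditional. If both eyes are counted and events arise only in treated eyes, reported percentages halve and the test is nearly unchanged at the lower rates examined; the loss of power grows at high event rates. If bilateral events are counted twice and tested as independent, type I error is inflated: about 21% instead of 1.5% at a 10% event rate when every event is bilateral, and about 8% to 16% for intermediate agreement at the 10% and 25% rates simulated. These figures assume 12 analysed subjects per arm, uncorrected chi-square and the illustrative rates above.

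The stronger conclusion, that the planned rate and test definitely use a wrong denominator, is not supported, because the plan states neither the denominator nor the unit of the test.

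**What to change.** Replace the two adverse-event sentences in section 8.3.1 with:

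> Adverse events are analysed per subject: the number and percentage of randomised subjects in each arm with at least one event of any kind, compared between arms. Ocular events in the treated right eye are also compared per subject (12 per arm). Events in the untreated left eye and non-ocular events are tabulated separately per subject, and the total number of events is listed.

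The any-event comparison keeps left-eye and systemic events in the between-arm analysis; the separate tables show where they occurred. The wording works whichever meaning of all eyes was intended and matches the participant unit in section 9.2. The cost is analysis-plan wording only: the event form already records laterality, so no new data, visits or subjects are needed.

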#### **Hypothesis:**

Ophthalmic gel PRO-167 has a safety and tolerability profile similar to that of its comparator in healthy subjects.

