# 5.5.3 Hypothesis

*Ha* Ophthalmic gel PRO-167 presents a safety and tolerability profile similar to the comparator in healthy subjects.

Ho Ophthalmic gel PRO-167 presents a safety and tolerability profile different from the comparator in healthy subjects.

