#### 6.4.1.2 Primary outcome variables of tolerability

- Burning
- Foreign body sensation
- Itching
- Eye comfort index

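### The safe-and-tolerable rule treats a non-significant difference at 12 per arm as similarity, with no margin: 1/12 v 5/12 (p = 0.059, Newcombe 95% CI -2 to +61 points) would pass as no statistical difference

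*Combined protocol and SAP*

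**What the plan says.** The decision rule is in section 8.3.1: "the investigational drug is safe and tolerable when there are no clinical and statistical differences in all the variables of primary outcome", relative to the comparator. The primary variables are three for safety in 6.4.1.1 (goblet cell density, epithelial defects, adverse events) and four for tolerability in 6.4.1.2 (burning, foreign body sensation, itching, eye comfort index).

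For quantitative variables 8.3.1 specifies "Inter-group analysis: Mann-Whitney U test". For qualitative variables the analysis "will be done creating 2x2 contingency tables", with "Difference between groups: test χ2 (Chi-square) of Pearson". Alpha is 0.05 throughout.

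The Summary hypothesis reads "Ophthalmic gel PRO-167 has a safety and tolerability profile similar to that of its comparator in healthy subjects". Section 5.5.3 makes that the alternative and states the null as "Ho Ophthalmic gel PRO-167 presents a safety and tolerability profile different from the comparator in healthy subjects".

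Sections 6.6 and 6.6.1 give 24 subjects, 12 per group, one eye each. The design is labelled exploratory (Summary and 5.6), and every specific objective in 5.5.2 is to describe.

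**The concern.** The hypotheses, the tests and the conclusion do not fit together. Both named tests can reject equality, but neither can reject difference, so none of the planned tests can support the alternative in 5.5.3. The rule closes the gap by reading failure to reject equality as evidence of similarity. That reading is weakest in small samples, where non-significance is the usual result even when the true difference is large.

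Nothing else in the plan repairs this:

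- No equivalence or non-inferiority margin and no confidence-interval criterion is given. The symbol δ appears in the sample-size formula in 6.6.1, but it has no value and the rule does not use it.
- A clinical difference has no threshold.
- It is unclear whether a clinical or a statistical difference alone blocks the claim, or only a difference that is both.
- The rule has no direction, so a significantly better result on PRO-167 would also break it.

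At stake is the trial's stated conclusion. The report could call PRO-167 safe and tolerable while the data remain compatible with a large excess of symptoms or events.

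**Working it through.** **Inputs from the documents.** 12 per arm (6.6.1); uncorrected Pearson chi-square and Mann-Whitney at 0.05 (8.3.1); seven primary variables (6.4.1.1 and 6.4.1.2). The plan gives no operating characteristic for the rule, so there is none to reproduce. The step to 24 subjects does reproduce: 19/(1 - 0.2) = 23.75, so 24. The 19 itself cannot be recomputed because δ has no value.

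**Step 1: single tables.** For counts a and b out of 12, chi-square = 24(a(12 - b) - b(12 - a))² / (12 × 12 × (a + b) × (24 - a - b)).

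- 1/12 v 5/12: 24 × (7 - 55)² / (144 × 6 × 18) = 55,296/15,552 = 3.556, p = 0.059.
- 0/12 v 3/12: 24 × 36² / (144 × 3 × 21) = 31,104/9,072 = 3.429, p = 0.064.
- The next counts up are significant: 1 v 6 gives p = 0.025 and 0 v 4 gives p = 0.029.

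**Step 2: what those tables allow.** Newcombe's interval combines the Wilson limits (l, u) of each arm: lower = d - √((p₁ - l₁)² + (u₂ - p₂)²), upper = d + √((u₁ - p₁)² + (p₂ - l₂)²).

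- For 5/12 the Wilson limits are 0.1933 and 0.6805; for 1/12 they are 0.0149 and 0.3539.
- Lower: 0.3333 - √(0.2234² + 0.2706²) = 0.333 - 0.351 = -0.018.
- Upper: 0.3333 + √(0.2638² + 0.0684²) = 0.333 + 0.273 = 0.606.
- For 3/12 minus 0/12 the same method gives -0.041 to 0.532.

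The method matters at this size. The simple Wald interval for 5/12 minus 1/12 is +1.4 to +65.3 points and just excludes zero. Fisher's exact test and the Yates correction give p of about 0.16, so either would make a finding of no difference easier still.

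**Step 3: power of one chi-square test.** Exact enumeration at 12 per arm, with 10% in the comparator (rates assumed):

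| PRO-167 rate | Power | All seven tests non-significant |
|---|---|---|
| 25% | 0.124 | 0.718 |
| 30% | 0.198 | 0.657 |
| 40% | 0.387 | 0.503 |
| 50% | 0.600 | 0.328 |

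**Step 4: the whole rule, statistical part only.** The last column assumes three Mann-Whitney tests of size 0.05 and four independent binary tests, one of them worsened. Chi-square size at 10% v 10% is 0.0149, so the probability is (1 - power) × (1 - 0.0149)³ × 0.95³. For 30%: 0.802 × 0.956 × 0.857 = 0.657.

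- Varying the split (3+4 or 2+5) and the correlation (0 or 0.6) gives 72-77%, 66-70%, 50-54% and 33-35% for the four rows.
- If all four binary variables go from 10% to 30%: 0.8022⁴ × 0.95³ = 0.355.
- With 19 evaluable subjects (10 v 9, the 3+4 split), the 25%, 30% and 40% rows become 67-72%, 61-67% and 48-55%, depending on which arm is smaller.

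**Step 5: an identical product.** At 10% rates it fails the statistical part with probability 1 - 0.9851⁴ × 0.95³ = 0.193. The range is 14-19% over the splits and correlations above, and about 10-35% when event rates also run from 3% to 50%.

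**The case against.** The strongest case is about proportion. This is an exploratory phase I trial in healthy subjects, with 10 days of treatment and the same active ingredient and strength in both arms. Early termination has its own criteria in 9.2, and large or multi-variable harm would usually be detected. That is true, and it means the defect is not a lack of oversight. It does not help the rule: the exploratory label and the descriptive objectives justify a small trial with a descriptive report, not a binary verdict drawn from non-significance.

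Second, the rule also mentions clinical differences, so 1/12 v 5/12 might fail on judgement. That is possible on one reading, but there is no threshold and the conjunction is ambiguous. The example shows only that the table is not a statistical difference.

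Third, the seven-test model is a construct. Symptoms have severity, frequency and diary versions, two stains are used, and there are two post-baseline visits. More tests would lower the non-significance figures and raise the false-failure figure. The 5% Mann-Whitney size is also generous: with 4%, the 10% lower end in Step 5 becomes about 8%. These points stand, so the Step 4 and Step 5 percentages hold only under that model.

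Fourth, the 25% in 6.6.1 is good tolerance and the 10% is bad tolerance, so they do not anchor a rise from 10% to 25%. That also stands; the rates are assumptions. None of these objections touches the single-table results or the mismatch between hypotheses and tests.

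**Conclusion.** The concern holds and must be fixed: the rule is wrong as written. Non-significance on tests of equality cannot support a similarity hypothesis, and no margin, interval criterion or clinical threshold fills the gap. The firmest measure of size needs no assumed event rate: with 12 per arm, tables whose Newcombe 95% intervals reach +61 points (1/12 v 5/12) or +53 points (0/12 v 3/12) pass as no statistical difference.

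The long-run figures are illustrations. They depend on assumed rates and on the seven-test model, and they cover only the statistical part of the rule. As probabilities that the claim would be allowed, they are upper bounds if a clinical difference alone also blocks it, and lower bounds if a difference must be both clinical and statistical to block it.

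**What to change.** In 8.3.1, delete the success rule that requires no differences across all primary variables. For each primary variable, report the PRO-167 minus comparator difference with its 95% CI, naming the method (Newcombe for proportions, for example), and treat p-values as descriptive. State that the conclusion will be that no difference was detected and similarity was not demonstrated, unless the interval lies within a margin fixed before enrolment. Define a clinical difference numerically or remove the term. Reword the Summary hypothesis and 5.5.3 to match, most simply as a descriptive aim in line with 5.5.2 and 5.6.

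The cost is wording and a few intervals; no subjects are added. The downside is that a similarity claim will probably not be met. At 12 per arm the Newcombe half-width is about 24 points for 0/12 v 0/12 and 28 points for 1/12 v 1/12. For a mean it is 2.074 × √(2/12) = 0.85 SD. With identical products at 10% rates, the interval falls inside an assumed ±25-point margin in 8% of trials, or 44% if only the unfavourable limit counts. For scale only, 80% power for that margin at 10% rates needs about 27 per arm (unfavourable side only) or 36 per arm (two-sided). Enlarging the trial is not proposed.
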